9.7.4. Handling of Missing Data

There will be no imputation or replacement of missing data. All analyses will be conducted on observed cases. All patients will be included in the descriptive analysis limited with the information recollect. The missing data will be included in the study report. Analysis with case complete will not be conducted.

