9.7.5.1. Descriptive statistics

Frequencies and percentages will be reported for binary and categorical variables, while medians and interquartile ranges (IQRs) will be reported for continuous variables, i.e., HRU. Finally, it will be presented through a tabular display of summary statistics and will be complemented by the generation of graphs, such as histograms, box plots, violin plots, density plots, scatterplots, depending on the nature of the variable.

On the other hand, difference of means (Student or Welch t-test) or medians (Wilcoxon or Kruskal-Wallí's test) between subgroups will be considered (according to the variable distribution – normal or not), considering the sizes of these groups and trends in the behavior of the measures of centrality and dispersion.

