9.7.5.2. Bivariate and multivariable analysis

This study does not evaluate any hypothesis. As exploratory analysis and if it is feasible with the number of patients enrolled and distribution of the studied variables, the analysis of the association of baseline characteristics with quality of life and cardiovascular functionality using bivariate and multivariate regression models will be conducted. In terms of distribution of studied continuous variables, a normal test will be conducted in order to determine if it requires a parametric or no parametric test. The test of normality used will be used, frequency distribution (histogram), boxplot, P-P plot (probability-probability plot), and Q-Q plot

PFIZER CONFIDENTIAL

CT24-WI-GL02-RF01 6.0 Non-Interventional Study Protocol Template For Primary Data Collection Study 01-

Aug-2023

Page 33 of 57

CLINICAL AND MEDICAL CONTROLLED DOCUMENT (CMCD) REQUIRED FORM/TEMPLATE

Identifier	Version	Title	Effective Date
CT24-WI-GL02-RF01	6.0	NON-INTERVENTIONAL STUDY PROTOCOL TEMPLATE FOR PRIMARY DATA COLLECTION STUDY	01-Aug-2023

(quantile-quantile plot) to assess normality visually and Kolmogorov-Smirnov (K-S) test and Shapiro-wilk test to evaluate directly (20).

For bivariate analysis, no-parametric tests are necessary due to the variables being of dependent nature by being repeated measures during the follow-up. For continuous variables, paired t-test and Wilcoxon signed ranks test will be used (21).

For multivariable analysis, mixed models will be used, repeated measures analysis of covariance with an unstructured covariance matrix, being patient as random effects and visit and baseline characteristics as fixed effects (22,23).

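### Observed-case KCCQ medians by nominal visit do not describe a within-patient two-year change, and the exploratory model and test rationale in Section 9.7.5.2 need correcting

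*Protocol*

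**What the plan says.** - **Objectives (Sections 8 and 9.7.1).** The primary objective is quality of life over two years. Change from baseline over 24 months is named without an estimator, and no hypothesis is tested. The exploratory objective relates baseline variables to changes in quality of life.
- **Missing data (9.7.4).** "There will be no imputation or replacement of missing data. All analyses will be conducted on observed cases". Also: "Analysis with case complete will not be conducted".
- **Description (9.7.5.1).** "medians and interquartile ranges (IQRs) will be reported for continuous variables".
- **Exploratory analysis (9.7.5.2).** It is conditional: "As exploratory analysis and if it is feasible with the number of patients enrolled and distribution of the studied variables". For the bivariate part it says that "no-parametric tests are necessary due to the variables being of dependent nature by being repeated measures during the follow-up", and the next sentence reads "For continuous variables, paired t-test and Wilcoxon signed ranks test will be used". The multivariable model is a "repeated measures analysis of covariance with an unstructured covariance matrix, being patient as random effects and visit and baseline characteristics as fixed effects".
- **Timing.** The index date is the first prescription (9.1). Patients qualify if prescribed before August 2023 (9.1), or treated between August 2022 and August 2023 (9.2). The KCCQ starts at consent. Collection runs from 15 November 2023 to 30 July 2025 (Section 6). Visits are every three months, plus or minus 15 days, up to month 24 (9.2). Follow-up ends earlier at death, withdrawal, end of treatment or loss (9.1).

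**The concern.** Every eligible prescription predates the first possible KCCQ by months, and by very different amounts. An observed-case median at a nominal visit then depends on who could have been scored at that visit as well as on how patients fared. Early visits hold only the most recently prescribed patients. Late visits hold only those alive, on treatment and still in the study. The primary objective could be reported as a sequence of medians that looks like a course over two years but is not one.

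The mixed model is the planned tool that could handle staggered entry. It is exploratory, its covariance is unclear or redundant, and it lacks the term that its own objective calls for. The bivariate paragraph gives a wrong reason for its choice of tests.

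**Working it through.** **1. Who can be scored at each visit.** The visit at month m is possible if index date + m months + 15 days is on or after 15 November 2023, and index date + m months − 15 days is on or before 30 July 2025. On 15 November 2023 a patient prescribed on 1 August 2022 is 15.5 months past index. One prescribed at the end of July 2023 is 3.5 months past it, and one at the end of August 2023 is 2.5 months past it. With N = 50 and uniform index dates (assumption), the largest possible numbers are:

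| Month | Last index date 31 July 2023 | Last index date 31 August 2023 |
|---|---|---|
| 0 | 0 | 0 |
| 3 | 0 | 3.9 |
| 6 | 12.6 | 15.5 |
| 9 | 25.1 | 27.0 |
| 12 | 37.5 | 38.5 |
| 15 to 21 | 50 | 50 |
| 24 | 50 | 48 |

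These are ceilings: everyone enrols on the first day and nobody is lost.

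**2. Span of a within-patient change.** In the first column, the first possible score falls at month 6, 9, 12 or 15 for 12.6, 12.5, 12.4 and 12.5 patients. Their spans to month 24 are 18, 15, 12 and 9 months. The mean is (12.6×18 + 12.5×15 + 12.4×12 + 12.5×9)/50 = 675.6/50 = 13.5 months, not 24.

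**3. Attrition.** Section 7 cites 29.5% mortality on tafamidis at 30 months. With a constant hazard (assumption), deaths by month 24 from index are 1 − 0.705^(24/30) = 24.4%, which leaves about 38 of 50. Enrolled patients have already survived to consent. Over 13.5 months the figure is 1 − 0.705^(13.5/30) = 14.6%, which leaves about 43.

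**4. Covariance.** An unstructured matrix for k visits has k(k+1)/2 parameters: 45 for nine, 36 for eight. At N = 50 and nine visits that is 1.1 patients per parameter. Of the 45 cells, 9 (all involving month 0) have no data. If month 3 is also empty, 9 + 8 = 17 have none. With a patient random intercept the marginal covariance is V = Σ + σ²J, where J is all ones. Replacing σ² by σ² − c and Σ by Σ + cJ leaves V unchanged. The model has 46 parameters with rank 45, so one is not identifiable.

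**5. Mean structure.** With main effects only, E(KCCQ at visit j) = μ_j + βx. The difference between visits j and k is μ_j − μ_k, free of x. So β describes level. If enrolment KCCQ is also a covariate, β becomes a shift in later scores that is the same at every visit, which still says nothing about course.

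**6. Tests.** A paired t-test deals with dependence by differencing, and it is parametric. It compares two occasions and contains no baseline characteristic, so it cannot assess the association that Section 9.7.5.2 sets out to study.

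**7. Size, for illustration only.** All inputs below are assumed.
- *Late entry, linear decline of 0.25 points per month (−6.0 over 24 months), dropout more likely at low scores.* The observed change from first score to month 24 was −2.69, or −3.29 with milder dependence. The true change over 13.5 months is −0.25 × 13.5 = −3.375. The error over the period observed is therefore 0.69 or 0.09 points. The shorter span explains 2.625/3.31 = 79%, or 2.625/2.71 = 97%, of the gap to −6.0.
- *No late entry, true change about −10, 24% to 40% missing at month 24.* The mean paired change was −8.7 to −9.8. The difference between per-visit medians was −0.9 to −6.6. An unstructured likelihood model gave −9.8 to −10.4.

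**The case against.** The protocol is not silent on timing. Section 9.1 says the analysis will take account of the prescription date, the start of tafamidis and the start of KCCQ measurement. Section 9.7.3.2 lists time on tafamidis before enrolment as a subgroup. Section 9.9 admits that baseline quality of life may be hard to measure. The study is descriptive, and the tests and model are exploratory and conditional on feasibility. These points stand. They limit the severity, but none provides a within-patient summary.

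Four stronger readings are tempting and are not supported.
- *The two-year change will be wrong by a known amount.* The document gives no input for this. In the illustrations most of the gap was simply the shorter span, and paired-change bias was small.
- *The paired tests are the primary KCCQ analysis.* They appear only in the exploratory section.
- *The paired tests contradict the ban on complete-case analysis.* Using available pairs at a visit is not the same as restricting to fully observed patients.
- *The model will fail or give biased results.* Redundancy threatens identifiability, not the mean change, and an unstructured fit behaved well in the second illustration, although that had no late entry. The text can also be read as an unstructured matrix for the random effects, which would not be redundant. It would then have to say which effects are random.

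A random-slope model is no cure either. In the first illustration it returned −5.09 and −5.85 against −6.0, but the simulated truth was linear. The real course in months 0 to 3 is essentially unobserved.

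**Conclusion.** The point holds as a matter of specification, not as a demonstrated bias. By the protocol's dates no KCCQ can fall at month 0 from index, and at most about 4 of 50 patients can have one at month 3. About 13 (up to about 16) of 50 can have one at month 6, and all 50 only from month 15. The zero at month 0 follows from the dates alone. The other counts assume uniform index dates. Observed-case medians by nominal visit therefore do not describe a within-patient two-year change.

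In Section 9.7.5.2 the rationale for non-parametric tests is wrong and conflicts with the test named next. The covariance is either redundant or unspecified, and main effects alone do not address how baseline variables relate to the course of KCCQ. The correction is worth making, but it is not critical because no formal decision rests on these analyses.

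**What to change.** - **Primary summary.** Report within-patient change in KCCQ-OS from the enrolment score, from a mixed model on all scores. Use actual time since treatment start (or index date, stating which), with 95% CI, over the period actually observed. Label any 24-month figure that reaches back to months 0 to 3 as extrapolated. Keep per-visit medians as description, with the number observed at each visit.
- **Covariance.** Use one specification: either random intercept and slope, or a residual matrix, not both.
- **Exploratory objective.** Adjust for enrolment KCCQ and add baseline characteristic × time.
- **Tests.** Delete the sentence that dependence requires non-parametric tests, and limit paired tests to describing change.

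The cost is protocol and analysis-plan wording and some programming, with no new data. The downside is reliance on missing at random and on a time course that cannot be checked in the unobserved early months. The model also does not define KCCQ after death.

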9.8. Quality control

Quality control for each project is performed by a specific audit team member assigned to the Study and the Monitoring and Data Quality Oversight plan (24).

Review of the data collected in the study for accuracy and consistency throughout the execution of the study is essential to ensure data quality and integrity. It will be led by a vendor responsible to monitor the collection of data and the established requirements in this protocol. Three monitoring is planned during the collection data. Each monitoring involves the validation of eligibility criteria, sign of informed consent, consistency, and accuracy of data from the data sources as is descriptive in the Monitoring and Data Quality Oversight plan. Additionally, a review of consistency of the behavior of collected data will be conducted after finalizing the collection data. It consists of validated outliers, data that are not consistent with the variable or missing data. In the case of any query of the data, it will be clarified to the sites (24).

Quality control practices include, but are not limited, to:

- Consistency checks of the anonymized database.
- Review of records and variables with less completeness.
- Having qualified individuals who did not have a role in the study review data analyses and any final study report documentation for accuracy.
- Statistical and econometric programming will be performed by experienced personnel with significant quantitative health care research experience and a thorough understanding of study design and analytic methods.
- Scripts will be reviewed by a second person with understanding of the study to ensure accuracy and validity of the code. This implies auditing all software programs and results both with respect to computer output and final tables.
- Ensuring proper documentation of data sources and key analytical steps.

PFIZER CONFIDENTIAL

CT24-WI-GL02-RF01 6.0 Non-Interventional Study Protocol Template For Primary Data Collection Study 01-

Aug-2023

Page 34 of 57

**CLINICAL AND MEDICAL CONTROLLED DOCUMENT (CMCD)
REQUIRED FORM/TEMPLATE**

Identifier	Version	Title	Effective Date
CT24-WI-GL02-RF01	6.0	NON-INTERVENTIONAL STUDY PROTOCOL TEMPLATE FOR PRIMARY DATA COLLECTION STUDY	01-Aug-2023

- All results will be evaluated for theoretical and logical soundness by multiple personnel, performing internal consistency checks of data presentations.
- Aligning dissemination materials with external requirements.

9.9. Limitations of the research methods

This study has the following limitations:

- The information of the patient in the baseline will be limited to data available in the clinical records and awareness of the patient.
- The complete information of hospitalizations will depend on the access to medical records provided by the patients.
- The number of patients recruited will likely be small which affects the subgroup analysis.
- The patients may have already started treatment prior to start of the study. This could make it difficult to adequately measure baseline QoL.
- Availability of 6 Minute walk test and scintigraphy for all patients during the follow-up due to the management of ATTR-CM patients have not been standardized.
- Although the official language of Colombia is Spanish, the languages and dialects of ethnic groups are also recognized as official. However, only around 5% of the population recognizes itself as belonging to an Indigenous or Rrom group (25).

9.10. Other aspects

Not applicable.

PFIZER CONFIDENTIAL

CT24-WI-GL02-RF01 6.0 Non-Interventional Study Protocol Template For Primary Data Collection Study 01-Aug-2023
Page 35 of 57

CLINICAL AND MEDICAL CONTROLLED DOCUMENT (CMCD) REQUIRED FORM/TEMPLATE

Identifier	Version	Title	Effective Date
CT24-WI-GL02-RF01	6.0	NON-INTERVENTIONAL STUDY PROTOCOL TEMPLATE FOR PRIMARY DATA COLLECTION STUDY	01-Aug-2023

10. PROTECTION OF HUMAN PARTICIPANTS

10.1. Patient information

All parties will comply with all applicable laws, including laws regarding the implementation of organizational and technical measures to ensure protection of patient personal data. Such measures will include omitting patient names or other directly identifiable data in any reports, publications, or other disclosures, except where required by applicable laws.

The personal data will be stored at the study site in encrypted electronic and/or paper form and will be password protected or secured in a locked room to ensure that only authorized study staff have access. The study site will implement appropriate technical and organizational measures to ensure that the personal data can be recovered in the event of disaster. In the event of a potential personal data breach, the study site shall be responsible for determining whether a personal data breach has in fact occurred and, if so, providing breach notifications as required by law.

To protect the rights and freedoms of natural persons with regard to the processing of personal data, when study data are compiled for transfer to Pfizer and other authorized parties, patient names will be removed and will be replaced by a single, specific, numerical code, based on a numbering system defined by Pfizer. All other identifiable data transferred to Pfizer or other authorized parties will be identified by this single, patient-specific code. The investigator site will maintain a confidential list of patients who participated in the study, linking each patient's numerical code to his or her actual identity. In case of data transfer, Pfizer will maintain high standards of confidentiality and protection of patients' personal data consistent with the clinical study agreement and applicable privacy laws.

10.2. Patient consent

The informed consent documents and any patient recruitment materials must be in compliance with local regulatory requirements and legal requirements, including applicable privacy laws.

The informed consent documents used during the informed consent process and any patient recruitment materials must be reviewed and approved by Pfizer, approved by the institutional review board (IRB)/independent ethics committee (IEC) before use, and available for inspection.

The investigator must ensure that each study patient is fully informed about the nature and objectives of the study, the sharing of data relating to the study and possible risks associated with participation, including the risks associated with the processing of the patient's personal data. The investigator further must ensure that each study patient is fully informed about his or her right to access and correct his or her personal data and to withdraw consent for the processing of his or her personal data.

Whenever consent is obtained from a patient's legally acceptable representative, the patient's assent (affirmative agreement) must subsequently be obtained when the patient has the

PFIZER CONFIDENTIAL

CT24-WI-GL02-RF01 6.0 Non-Interventional Study Protocol Template For Primary Data Collection Study 01-

Aug-2023

Page 36 of 57

CLINICAL AND MEDICAL CONTROLLED DOCUMENT (CMCD) REQUIRED FORM/TEMPLATE

Identifier	Version	Title	Effective Date
CT24-WI-GL02-RF01	6.0	NON-INTERVENTIONAL STUDY PROTOCOL TEMPLATE FOR PRIMARY DATA COLLECTION STUDY	01-Aug-2023

capacity to provide assent, as determined by the IRB/IEC. If the investigator determines that a patient's decisional capacity is so limited that he or she cannot reasonably be consulted, then, as permitted by the IRB/IEC and consistent with local regulatory and legal requirements, the patient's assent may be waived with source documentation of the reason assent was not obtained. If the study patient does not provide his or her own consent, the source documents must record why the patient did not provide consent (e.g., minor, decisionally impaired adult), how the investigator determined that the person signing the consent was the patient's legally acceptable representative, the consent signer's relationship to the study patient (e.g., parent, spouse), and that the patient's assent was obtained or waived. If assent is obtained verbally, it must be documented in the source documents.

10.3. Patient withdrawal

Patients may withdraw from the study at any time at their own request, or they may be withdrawn at any time at the discretion of the investigator or sponsor for safety, behavioral, or administrative reasons. In any circumstance, every effort should be made to document patient outcome, if applicable. The investigator would inquire about the reason for withdrawal and follow-up with the patient regarding any unresolved adverse events.

If the patient withdraws from the study, and also withdraws consent for disclosure of future information, no further evaluations should be performed, and no additional data should be collected. The sponsor may retain and continue to use any data collected before such withdrawal of consent.

10.4. Institutional review board (IRB)/Independent ethics committee (IEC)

It is the responsibility of the investigator to have prospective approval of the study protocol, protocol amendments, and informed consent forms, and other relevant documents, (e.g., recruitment advertisements), if applicable, from the IRB/IEC. All correspondence with the IRB/IEC should be retained by the investigator. Copies of IRB/IEC approvals should be forwarded to Pfizer.

10.5. Ethical conduct of the study

The study will be conducted in accordance with legal and regulatory requirements, as well as with scientific purpose, value and rigor and follow generally accepted research practices described in Guidelines for Good Pharmacoepidemiology Practices (GPP) issued by the International Society of Pharmacoepidemiology (ISPE), Good Practices for Outcomes Research issued by the International Society for Pharmacoeconomics and Outcomes Research (ISPOR), Good practices for real-world data studies of treatment and/or comparative effectiveness: Recommendations from the joint ISPOR-ISPE Special Task Force on real-world evidence in health care decision making, International Ethical Guidelines for Epidemiological Studies issued by the Council for International Organizations of Medical Sciences (CIOMS).

The study will be submitted to the IEC in the category of research minimal risk. The ethical principles of justice, beneficence, non-maleficence, and confidentiality of information

PFIZER CONFIDENTIAL

CT24-WI-GL02-RF01 6.0 Non-Interventional Study Protocol Template For Primary Data Collection Study 01-

Aug-2023

Page 37 of 57

**CLINICAL AND MEDICAL CONTROLLED DOCUMENT (CMCD)
REQUIRED FORM/TEMPLATE**

Identifier	Version	Title	Effective Date
CT24-WI-GL02-RF01	6.0	NON-INTERVENTIONAL STUDY PROTOCOL TEMPLATE FOR PRIMARY DATA COLLECTION STUDY	01-Aug-2023

established by the Declaration of Helsinki will be followed, in accordance with Resolution No. 8430 of 1993 of the Ministry of Health of Colombia.

PFIZER CONFIDENTIAL

CT24-WI-GL02-RF01 6.0 Non-Interventional Study Protocol Template For Primary Data Collection Study 01-Aug-2023
Page 38 of 57

**CLINICAL AND MEDICAL CONTROLLED DOCUMENT (CMCD)
REQUIRED FORM/TEMPLATE**

Identifier	Version	Title	Effective Date
CT24-WI-GL02-RF01	6.0	NON-INTERVENTIONAL STUDY PROTOCOL TEMPLATE FOR PRIMARY DATA COLLECTION STUDY	01-Aug-2023

11. MANAGEMENT AND REPORTING OF ADVERSE EVENTS/ADVERSE REACTIONS

REQUIREMENTS

The table below summarizes the requirements for recording safety events on the CRF and for reporting safety events on the non-interventional study (NIS) adverse event monitoring (AEM) Report Form to Pfizer Safety. These requirements are delineated for three types of events: (1) serious adverse events (SAEs); (2) non-serious AEs (as applicable); and (3) scenarios involving drug exposure, including exposure during pregnancy, exposure during breast feeding, medication error, overdose, misuse, extravasation, lack of efficacy, and occupational exposure. These events are defined in the section “Definitions of safety events.”

Safety event	Recorded on the CRF	Reported on the NIS AEM Report Form to Pfizer Safety within 24 hours of awareness
SAE	All	All
Non-serious AE	All	None
Scenarios involving exposure to a drug under study, including exposure during pregnancy, exposure during breast feeding, medication error, overdose, misuse, extravasation, lack of efficacy, and occupational exposure	All (regardless of whether associated with an AE), except occupational exposure	All (regardless of whether associated with an AE) Note: Any associated AE is reported together with the exposure scenario.

For each AE, the investigator must pursue and obtain information adequate both to determine the outcome of the AE and to assess whether it meets the criteria for classification as a SAE (refer to section "Serious Adverse Events" below).

Safety events listed in the table above must be reported to Pfizer within 24 hours of awareness of the event by the investigator **regardless of whether the event is determined by the investigator to be related to tafamidis**. In particular, if the SAE is fatal or life-threatening, notification to Pfizer must be made immediately, irrespective of the extent of available event information. This timeframe also applies to additional new (follow-up) information on

PFIZER CONFIDENTIAL

CT24-WI-GL02-RF01 6.0 Non-Interventional Study Protocol Template For Primary Data Collection Study 01-

Aug-2023

Page 39 of 57

**CLINICAL AND MEDICAL CONTROLLED DOCUMENT (CMCD)
REQUIRED FORM/TEMPLATE**

Identifier	Version	Title	Effective Date
CT24-WI-GL02-RF01	6.0	NON-INTERVENTIONAL STUDY PROTOCOL TEMPLATE FOR PRIMARY DATA COLLECTION STUDY	01-Aug-2023

previously forwarded safety event reports. In the rare situation that the investigator does not become immediately aware of the occurrence of a safety event, the investigator must report the event within 24 hours after learning of it and document the time of his/her first awareness of the events.

For safety events that are considered serious or that are identified in the far-right column of the table above that are reportable to Pfizer within 24 hours of awareness, the investigator is obligated to pursue and to provide any additional information to Pfizer in accordance with this 24-hour timeframe. In addition, an investigator may be requested by Pfizer to obtain specific follow-up information in an expedited fashion. This information is more detailed than that recorded on the CRF. In general, this will include a description of the AE in sufficient detail to allow for a complete medical assessment of the case and independent determination of possible causality. Any information relevant to the event, such as concomitant medications and illnesses, must be provided. In the case of a patient death, a summary of available autopsy findings must be submitted as soon as possible to Pfizer or its designated representative.

Reporting period

For each patient, the safety event reporting period begins at the time of the patient's first dose of tafamidis or the time of the patient's informed consent if s/he is being treated with tafamidis at study start, and lasts through the end of the observation period of the study, which must include at least 28 calendar days following the last administration of a drug under study; a report must be submitted to Pfizer Safety (or its designated representative) for any of the types of safety events listed in the table above occurring during this period. If a patient was administered a drug under study on the last day of the observation period, then the reporting period should be extended for 28 calendar days following the end of observation. Most often, the date of informed consent is the same as the date of enrollment. In some situations, there may be a lag between the dates of informed consent and enrollment. In these instances, if a patient provides informed consent but is never enrolled in the study (e.g., patient changes his/her mind about participation, failed screening criteria"), the reporting period ends on the date of the decision to not enroll the patient.

If the investigator becomes aware of a SAE occurring at any time after completion of the study and s/he considers the SAE to be related to tafamidis, the SAE also must be reported to Pfizer Safety.

Causality assessment

The investigator is required to assess and record the causal relationship. For all AEs, sufficient information should be obtained by the investigator to determine the causality of each AE. For AEs with a causal relationship to tafamidis follow-up by the investigator is required until the event and/or its sequelae resolve or stabilize at a level acceptable to the investigator, and Pfizer concurs with that assessment.

PFIZER CONFIDENTIAL

CT24-WI-GL02-RF01 6.0 Non-Interventional Study Protocol Template For Primary Data Collection Study 01-

Aug-2023

Page 40 of 57

**CLINICAL AND MEDICAL CONTROLLED DOCUMENT (CMCD)
REQUIRED FORM/TEMPLATE**

Identifier	Version	Title	Effective Date
CT24-WI-GL02-RF01	6.0	NON-INTERVENTIONAL STUDY PROTOCOL TEMPLATE FOR PRIMARY DATA COLLECTION STUDY	01-Aug-2023

An investigator's causality assessment is the determination of whether there exists a reasonable possibility that tafamidis caused or contributed to an AE. If the investigator's final determination of causality is "unknown" and s/he cannot determine whether tafamidis caused the event, the safety event must be reported within 24 hours.

If the investigator cannot determine the etiology of the event but s/he determines that *tafamidis* did not cause the event, this should be clearly documented on the *CRF* and the *NIS AEM Report Form*.

DEFINITIONS OF SAFETY EVENTS

Adverse events

An AE is any untoward medical occurrence in a patient administered a medicinal product. The event need not necessarily have a causal relationship with the product treatment or usage. Examples of AEs include but are not limited to:

- Abnormal test findings (see below for circumstances in which an abnormal test finding constitutes an AE);
- Clinically significant signs and symptoms;
- Changes in physical examination findings;
- Hypersensitivity;
- Progression/worsening of underlying disease;
- Lack of efficacy;
- Drug abuse;
- Drug dependency.

Additionally, for medicinal products, they may include the signs or symptoms resulting from:

- Drug overdose;
- Drug withdrawal;
- Drug misuse;
- Off-label use;
- Drug interactions;
- Extravasation;
- Exposure during pregnancy;
- Exposure during breast feeding;

PFIZER CONFIDENTIAL

CT24-WI-GL02-RF01 6.0 Non-Interventional Study Protocol Template For Primary Data Collection Study 01-

Aug-2023

Page 41 of 57

**CLINICAL AND MEDICAL CONTROLLED DOCUMENT (CMCD)
REQUIRED FORM/TEMPLATE**

Identifier	Version	Title	Effective Date
CT24-WI-GL02-RF01	6.0	NON-INTERVENTIONAL STUDY PROTOCOL TEMPLATE FOR PRIMARY DATA COLLECTION STUDY	01-Aug-2023

- Medication error;
- Occupational exposure.

Abnormal test findings

The criteria for determining whether an abnormal objective test finding should be reported as an AE are as follows:

- Test result is associated with accompanying symptoms, and/or
- Test result requires additional diagnostic testing or medical/surgical intervention, and/or
- Test result leads to a change in study dosing or discontinuation from the study, significant additional concomitant drug treatment, or other therapy, and/or
- Test result is considered to be an AE by the investigator or sponsor.

Merely repeating an abnormal test, in the absence of any of the above conditions, does not constitute an AE. Any abnormal test result that is determined to be an error does not require reporting as an AE.

Serious adverse events

A SAE is any untoward medical occurrence in a patient administered a medicinal or nutritional product (including pediatric formulas) at any dose that:

- Results in death;
- Is life-threatening;
- Requires inpatient hospitalization or prolongation of hospitalization (see below for circumstances that do not constitute AEs);
- Results in persistent or significant disability/incapacity (substantial disruption of the ability to conduct normal life functions);
- Results in congenital anomaly/birth defect.

Medical and scientific judgment is exercised in determining whether an event is an important medical event. An important medical event may not be immediately life-threatening and/or result in death or hospitalization. However, if it is determined that the event may jeopardize the patient or may require intervention to prevent one of the other outcomes listed in the definition above, the important medical event should be reported as serious.

Examples of such events are intensive treatment in an emergency room or at home for allergic bronchospasm; blood dyscrasias or convulsions that do not result in hospitalization; or development of drug dependency or drug abuse.

PFIZER CONFIDENTIAL

CT24-WI-GL02-RF01 6.0 Non-Interventional Study Protocol Template For Primary Data Collection Study 01-

Aug-2023

Page 42 of 57

**CLINICAL AND MEDICAL CONTROLLED DOCUMENT (CMCD)
REQUIRED FORM/TEMPLATE**

Identifier	Version	Title	Effective Date
CT24-WI-GL02-RF01	6.0	NON-INTERVENTIONAL STUDY PROTOCOL TEMPLATE FOR PRIMARY DATA COLLECTION STUDY	01-Aug-2023

Additionally, any suspected transmission via a Pfizer product of an infectious agent, pathogenic or non-pathogenic, is considered serious. The event may be suspected from clinical symptoms or laboratory findings indicating an infection in a patient exposed to a Pfizer product. The terms “suspected transmission” and “transmission” are considered synonymous. These cases are considered unexpected and handled as serious expedited cases by pharmacovigilance (PV) personnel. Such cases are also considered for reporting as product defects, if appropriate.

Hospitalization

Hospitalization is defined as any initial admission (even if less than 24 hours) to a hospital or equivalent healthcare facility or any prolongation to an existing admission. Admission also includes transfer within the hospital to an acute/intensive care unit (e.g., from the psychiatric wing to a medical floor, medical floor to a coronary care unit, neurological floor to a tuberculosis unit). An emergency room visit does not necessarily constitute a hospitalization; however, an event leading to an emergency room visit should be assessed for medical importance.

Hospitalization in the absence of a medical AE is not in itself an AE and is not reportable. For example, the following reports of hospitalization without a medical AE are not to be reported.

- Social admission (e.g., patient has no place to sleep)
- Administrative admission (e.g., for yearly exam)
- Optional admission not associated with a precipitating medical AE (e.g., for elective cosmetic surgery)
- Hospitalization for observation without a medical AE
- Admission for treatment of a pre-existing condition not associated with the development of a new AE or with a worsening of the pre-existing condition (e.g., for work-up of persistent pre-treatment lab abnormality)

Scenarios necessitating reporting to Pfizer Safety within 24 hours

Scenarios involving exposure during pregnancy, exposure during breastfeeding, medication error, overdose, misuse, extravasation, lack of efficacy, and occupational exposure are described below.

Exposure during pregnancy

An exposure during pregnancy (EDP) occurs if:

1. A female becomes, or is found to be, pregnant either while receiving or having been exposed to (e.g., environmental) tafamidis, or the female becomes, or is found to be, pregnant after discontinuing and/or being exposed to tafamidis (maternal exposure).

PFIZER CONFIDENTIAL

CT24-WI-GL02-RF01 6.0 Non-Interventional Study Protocol Template For Primary Data Collection Study 01-

Aug-2023

Page 43 of 57

**CLINICAL AND MEDICAL CONTROLLED DOCUMENT (CMCD)
REQUIRED FORM/TEMPLATE**

Identifier	Version	Title	Effective Date
CT24-WI-GL02-RF01	6.0	NON-INTERVENTIONAL STUDY PROTOCOL TEMPLATE FOR PRIMARY DATA COLLECTION STUDY	01-Aug-2023

An example of environmental exposure would be a case involving direct contact with a Pfizer product in a pregnant woman (e.g., a nurse reports that she is pregnant and has been exposed to chemotherapeutic products).

2. A male has been exposed, either due to treatment or environmental exposure to tafamidis to or around the time of conception and/or is exposed during the partner pregnancy (paternal exposure).

For exposure during pregnancy in studies of pregnant women, data on the exposure to drug during pregnancy, are not reportable unless associated with serious or non-serious adverse events.

As a general rule, prospective and retrospective exposure during pregnancy reports from any source are reportable irrespective of the presence of an associated AE and the procedures for SAE reporting should be followed, with the exception of those studies conducted in pregnant women (as described in above), for which data on the exposure are not reportable unless associated with serious or non-serious adverse events.

If a study participant or study participant's partner becomes, or is found to be, pregnant during the study participant's treatment with tafamidis this information must be submitted to Pfizer, irrespective of whether an AE has occurred using the NIS AEM Report Form and the EDP Supplemental Form.

In addition, the information regarding environmental exposure to tafamidis in a pregnant woman (e.g., a patient reports that she is pregnant and has been exposed to a cytotoxic product by inhalation or spillage) must be submitted using the NIS AEM Report Form and the EDP Supplemental Form. This must be done irrespective of whether an AE has occurred.

Information submitted should include the anticipated date of delivery (see below for information related to termination of pregnancy).

